Design: Randomized, double-blind, placebo-controlled trial of pre- and postoperative intravaginal estrogen therapy in 222 postmenopausal women with symptomatic prolapse undergoing a standardized surgical repair using native tissue.

Primary outcome: prolapse recurrence as defined by a composite of objective prolapse beyond the hymen, subjective/symptomatic prolapse (feeling of a bulge or *no change* or *worse* on the patient's global impression of improvement), or retreatment (e.g., reoperation or pessary use) assessed 1 year postoperatively. *Time to failure* will be compared in the two groups.

Important secondary outcomes assessing for changes in overactive bladder and urinary incontinence symptoms will be made by comparing symptoms (validated questionnaires) from Baseline to Pre-op/time of surgery. Aim 3 (see above, histomorphology, connective tissue studies) will be assessed from full thickness anterior apical vaginal wall biopsies taken at the time of surgery.

Interventions and Duration

Intervention: 1g conjugated estrogen (CE) cream (Premarin®, Pfizer Inc.) given nightly for 2 weeks then twice-weekly to complete planned 6-8 weeks (5 weeks minimum) therapy before a standardized uterosacral or sacrospinous ligament suspension transvaginal prolapse repair surgery. Those with a uterus will undergo concomitant total vaginal hysterectomy first. Twice-weekly CE cream application is then resumed upon discharge and continued for 1 year postoperatively.

Comparator: placebo vaginal cream, same schedule

Duration: The primary outcome of prolapse recurrence is assessed at one year postoperatively with continued surveillance of participants until 3 years postoperatively.

Sample Size and Population

Total sample size: N=222; 111 per treatment group

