9.4.2 Secondary outcomes

Aim 2: Quantify the effects of vaginal estrogen on symptoms of overactive bladder and urinary incontinence (**Subaim 2a**) and sexual function and dyspareunia (**Subaim 2b**) using validated questionnaires at regular intervals (Fig.3, Table 2) and assess for differences in rate of postoperative cystitis (**Subaim 2c**), and symptomatic vulvovaginal atrophy (**Subaim 2d**)

TABLE 2. Questionnaires Description

Pelvic Floor Distress Inventory (PFDI-20) ⁷³ (Aim 2a)	There are 3 scales (urinary, POP, and colorectal-anal symptom distress inventories) including questions about incomplete bladder emptying, urinary frequency, urgency, and urge- and stress-associated incontinence
Pelvic Floor Impact Questionnaire (PFIQ-7) ⁷³ (Aim 2a)	3 scales measure disease-specific impact on QoL (Incontinence, POP, and Colorectal-Anal) with questions about effect on physical activity, social activities, and emotional health.
Pelvic Organ Prolapse/Urinary Incontinence Sexual Function Questionnaire (PISQ-IR) ⁷⁴ (Aim2b)	Specifically assesses the impacts of PFDs (urinary incontinence and POP) on sexual health and includes questions quantifying sexual desire, arousal, orgasm, satisfaction, and pain associated with intercourse.
SF-12	Validated, commonly-used QoL questionnaire assessing overall mental and physical health
Patient Global Impression of Improvement & Severity (PGI-I, PGI-S) ⁷⁰	1-question tools validated for urinary incontinence and modified for POP. Assess overall impression of resolution of symptom bother and symptom severity related to POP.

Subaim 2a (changes in overactive bladder symptoms) will draw from the relevant questions on from the PFDI-20 and PFIQ-7. Information on stress urinary incontinence will stem from the relevant questions (PFDI-20 and PFIQ-7) completed at baseline and at the Pre-op visit.

Use of CE cream and conversion of inelastic, avascular, thin epithelium to a thicker, well-rugated epithelium corresponding to decreased pH could reduce the incidence of postoperative cystitis (**Subaim 2c**), which is common after genitourinary surgery (14% after USLS, defined by +culture within 1mo post-op)⁸⁴. This study will use a more liberal definition of post-op cystitis to include any prescription of antibiotics (culture-driven or empiric) for cystitis symptoms in the first postoperative month.

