9.5 Data Analyses

Aim 1. The **primary outcome** will be analyzed according to the assigned treatment group (modified intention-to-treat): i.e., all participants that are randomized *and* undergo a surgical prolapse repair *and* have at least one postoperative assessment will be analyzed according to their randomized assignment group. All eligible subjects who consent to the study and are enrolled will be available for analysis of baseline characteristics, and those that are randomized and use their study drug will be monitored for adverse events, but they must meet the additional qualifications above (i.e., undergo surgery and have a postoperative assessment) to be analyzed for the primary study outcome. At baseline, continuous measures will be compared between groups with Student's t-test and chi-square (or Fisher's exact test) for categorical measures. Scores from repeated surveys are continuous outcomes data and will be analyzed using repeated measures analysis of variance. We will test for interactions between time effect and treatment effect. For categorical data (e.g. prolapse stage), the analysis will be by categorical data modeling using weighted least squares and mixed logit models, with cross-sectional assessments (at specific time intervals) by chi-square. For missing follow-up points there are two possible approaches: (i) if there are few missing follow-up points, then their values may be imputed through multiple imputation methods, in which case repeated measures analysis of variance may be used following multiple imputation; (ii) more likely, we will make time a random effect and a mixed effects model with repeated measures will be applied. Time-to-event or event-free-time will be analyzed using survival methods to include the log-rank test and Cox regression. For measures that may not be assumed normal, the data will be transformed using a rank transformation prior to analysis.

In accordance with NIH policy, we will include an analysis of the intervention effect (CE cream) performed by racial/ethnic subgroups, recognizing that the analyses will not have high statistical power for detecting clinically meaningful differences between races/ethnicities.

Aim 2 Outcomes. As above, continuous scores from repeated surveys will be analyzed using repeated measures analysis of variance with appropriate corrections made, as necessary, for missing data.

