Subaim 2a & 2b. Assuming a baseline UDI-6 score (*obtained from the PFDI-20*) of 7.90 ± 1.91 for the stress-incontinent subpopulation of IMPROVE (expected to be at least 60%, or 67 participants per study arm)¹⁰⁵, in order to demonstrate a clinically meaningful improvement (decrease) of $0.5(\text{SD})^{106}$ to 6.95 ± 1.91 using CE cream from baseline to time of surgery (preop), with 80% power and $\alpha 0.05$, 65 participants are needed per arm. Further, to demonstrate an improvement in a baseline IIQ-7 score (*obtained from the PFIQ-7*) of 9.67 ± 7.14^{105} to 6.12 ± 7.1 , 64 participants are needed per arm (Subaim 2a). Similarly, to find a clinically important improvement (increase) in overall PISQ-12 score from baseline 25.0 ± 4.95 (women with prolapse¹⁰⁷) to 27.48 ± 4.95 at preop (or any postoperative time point), 64 participants are needed per arm (Subaim 2b). Thus, enrollment goals designed to address the primary aim (Aim 1) are sufficient to address these important secondary aims.

Because midurethral slings and anticholinergic or beta-3 agonist medications are not excluded in study participants, these other interventions will clearly impact upon

incontinence rates and will be controlled for in statistical comparisons between the two groups. Gross estimates of overactive bladder in the 2 groups will also be assessed by rates of anticholinergic or beta agonist use, as medication history will be queried at each patient encounter. Modest improvements in *stress* and overall urinary incontinence will be assessed from baseline to Pre-op (i.e. approximately 6-8wks local estrogen) using the relevant PFDI-20 and PFIQ-7 questions (see above Analyses) at both time points.

Subaim 2c. Proportions of participants with postoperative cystitis will be compared using chi-square. Using the liberal definition of post-operative cystitis to include any patient prescribed antibiotics for cystitis symptoms, this study will have sufficient power to demonstrate an improvement from a 22% cystitis rate to 10% (80% power, α 0.05). The postoperative “MedSurg” history form (**Form 15**) queries whether there has been any interval occurrence of urinary tract infection (Item B4) and whether symptoms were treated empirically (i.e., no urine culture) or if culture-proven.

Subaim 2d. Comparisons of vaginal maturation index and atrophy symptoms will use analysis of covariance, with treatment and study center as factors and baseline values as the covariate.

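### Subaims 2a and 2b: the plan does not say how the baseline score enters; using it as an ANCOVA covariate, as Subaim 2d does, gains precision at no extra data cost

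*Combined protocol and SAP*

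**What the plan says.** Section 9.5 (Aim 2 Outcomes) states that "continuous scores from repeated surveys will be analyzed using repeated measures analysis of variance" and refers back to the Aim 1 text. That text adds: "We will test for interactions between time effect and treatment effect". If follow-up points are missing, it continues, "more likely, we will make time a random effect and a mixed effects model with repeated measures will be applied". None of this says whether the baseline score is one of the repeated outcomes or a covariate.

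The contrast for Subaim 2a is clear. The Précis describes "comparing symptoms (validated questionnaires) from Baseline to Pre-op/time of surgery", and section 9.4.2 draws the stress-incontinence information from questions "completed at baseline and at the Pre-op visit".

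The sizing paragraph for Subaims 2a and 2b takes UDI-6 from 7.90 to 6.95 with SD 1.91 at both points and concludes that "65 participants are needed per arm". The stress-incontinent group is "expected to be at least 60%, or 67 participants per study arm". The same paragraph says that slings and overactive-bladder drugs will be adjusted for. Only Subaim 2d is given an analysis of covariance, with treatment and center as factors and the baseline value as covariate.

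**The concern.** With two visits, the time-by-treatment test in a repeated-measures ANOVA is algebraically a t-test on change scores. Its variance depends on the correlation between the baseline and Pre-op scores. The sizing ignores that correlation, because it compares scores at a single visit. The analysis text and the sample size therefore describe different tests, which coincide at only one value of a quantity that the plan does not give.

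Power for a named secondary aim is at stake. If the correlation is low, a change-score test adds baseline noise to the comparison. ANCOVA is more precise than the change score at every correlation below 1. It is also more precise than the post score alone whenever the correlation is not zero, apart from one degree of freedom. The baseline score is already collected.

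**Working it through.** **Inputs.** UDI-6 difference δ = 7.90 − 6.95 = 0.95; SD σ = 1.91 at both visits; 80% power and α = 0.05 (section 9.5; two-sided is assumed because one-sided gives about 50 per arm and does not fit). The baseline to Pre-op correlation ρ is not in the documents; I assume 0.3, 0.5 and 0.7.

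**Reproducing the plan's figure.** n per arm = 2(1.96 + 0.8416)² × (1.91/0.95)² = 15.70 × 4.042 = 63.5, so 64 by the normal approximation. The exact t-test gives 64.4, so 65, as stated. The 65 is thus a two-sample t-test on single-visit scores.

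**Variance of each analysis, as a multiple of σ².**
- Post score only: 1
- Change score (two-visit time-by-treatment test): 2(1 − ρ)
- ANCOVA: 1 − ρ²

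The change score matches the post score only when 2(1 − ρ) = 1, that is, ρ = 0.5. ANCOVA relative to change is (1 − ρ²)/[2(1 − ρ)] = (1 + ρ)/2 = 0.65/0.75/0.85 at ρ = 0.3/0.5/0.7.

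**n per arm for 80% power (t-based).**

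| ρ | Post only | Change | ANCOVA |
|---|---|---|---|
| 0.3 | 65 | 90 | 59 |
| 0.5 | 65 | 65 | 49 |
| 0.7 | 65 | 40 | 34 |

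Check at ρ = 0.3 by the normal formula: 63.5 × 1.4 = 88.9 and 63.5 × 0.91 = 57.8; the t-correction adds about one to each after rounding up.

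**Power at the available numbers.** 60% of 111 is 66.6, the plan's 67. If the 15% pre-surgery loss in section 9.2 also removes Pre-op scores, 94 per arm remain and 60% of 94 is 56.4, so 56. Power is from the noncentral t with noncentrality [δ/(σ√f)]√(n/2), where f is the variance factor. At 67 per arm and ρ = 0.3, this is 0.4974/√1.4 × √33.5 = 2.43 for change and 0.4974/√0.91 × √33.5 = 3.02 for ANCOVA. Against a critical value of 1.98, these give about 68% and 85%.

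| n per arm | ρ | Post only | Change | ANCOVA |
|---|---|---|---|---|
| 67 | 0.3 | 81.5% | 67.6% | 85.0% |
| 67 | 0.5 | 81.5% | 81.5% | 91.0% |
| 67 | 0.7 | 81.5% | 95.8% | 97.9% |
| 56 | 0.3 | 74.2% | 59.7% | 78.1% |
| 56 | 0.5 | 74.2% | 74.2% | 85.4% |
| 56 | 0.7 | 74.2% | 92.0% | 95.5% |

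At 56 per arm, the change score reaches 80% at ρ of about 0.57 and ANCOVA at about 0.37.

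A simulation of 4,000 trials per correlation at 65 per arm gave post/change/ANCOVA power of 80/67/84%, 81/80/90% and 81/95/97% at ρ = 0.3, 0.5 and 0.7. All three estimators centred within 0.01 of the true 0.95, so none is biased.

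**IIQ-7** (difference 3.55, average SD 7.12) behaves alike: at 65 per arm, change 66/81/95% and ANCOVA 84/90/98%.

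**Subaim 2b.** On the plan's PISQ-12 inputs (2.48, SD 4.95), with all 94 per arm contributing, change-score power is 82/93/99% and ANCOVA power 95/98/99.8%.

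**The case against.** The strongest reply is that no error is shown. The plan never mentions a change score; it sizes on single-visit scores and says that a mixed model is more likely. A change-score test has the correct size and is unbiased, and at a correlation of 0.5 the stated 65 is right. At 0.7 both tests are well powered. This stands: the change-score reading is an inference, and the point concerns efficiency.

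It does not remove the case for stating the analysis. If a post-score comparison was meant, ANCOVA still improves on it at each correlation examined. The mixed model secures the gain only if baseline is a covariate or the arms' baseline means are constrained equal, and section 9.5 says neither.

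A reader might infer from the 56-per-arm rows that 2a is underpowered. The documents do not establish that. The 60% is a floor, and Pre-op scores are taken before surgery, so a woman who attends that visit but has no operation can still contribute. Those rows are a worst case, and there even the post score has only 74%, so part of the deficit comes from attrition and not from the choice of analysis.

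A reader might also extend the shortfall to 2b. At 94 per arm the plan's own inputs show none. They are also PISQ-12 figures, whereas the scheduled instrument is PISQ-IR, so they do not directly describe the data to be collected.

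**Conclusion.** The concern holds as an improvement in precision for Subaims 2a and 2b. The direction is certain: relative to a change score, ANCOVA cuts the variance by 35/25/15% at correlations of 0.3/0.5/0.7. The size for this trial cannot be fixed, because the correlation is not documented. At 67 per arm, the UDI-6 gain over the change score is about 17, 9 and 2 percentage points; over the post score alone it is about 3, 9 and 16. Only a correlation a little below 0.5 or lower takes the change score under 80% at 67 per arm.

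The figures assume normally distributed scores, equal SDs at the two visits and no rank transformation, which section 9.5 allows for non-normal measures. It would go too far to say that the planned analysis is invalid, that it is definitely a change-score test, or that either subaim is shown to be underpowered.

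**What to change.** In section 9.5, state for Subaims 2a and 2b that the Pre-op score is compared by ANCOVA with treatment as a factor, the baseline score as covariate and study center as in 2d. Preferably include all three randomisation factors (site, hysterectomy status, duration since menopause); this goes beyond the 2d wording, so it must be written out. Where several visits are analysed, use a mixed model of the post-baseline scores with the same covariates, or one with baseline means constrained equal across arms.

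Reconcile this with the sentence promising control for slings and bladder medications. Slings are placed at surgery, after the Pre-op score, so they cannot affect that comparison. Medication started after randomisation may itself reflect treatment and should not silently enter the main model; an adjusted analysis can be labelled as supportive. Also state how missing baseline scores are handled.

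The cost is SAP wording. No extra visits or participants are needed. The full model spends five degrees of freedom (baseline 1, site 2, hysterectomy 1, menopause 1) instead of one, which changes power by about 0.1 percentage point.

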6.2.2 Enrollment, Baseline, and/or Randomization

Enrollment

In this study, a single informed consent will encompass both screening and study procedures (as screening procedures are a part of routine care). Enrollment and randomization will occur on the same day all screening criteria are met and the individual agrees to participate. This enrollment/randomization date will be captured on a case report form at the *Baseline assessment*.

Baseline Assessments

- Contact Information (**Form 01**): name, address, phone, email data from patient and an alternative contact. Confirm patient's assent to being contacted by text and/or email.
- Demographics (**Form 02**): racial/ethnicity data and type of health insurance payer
- Medical History (**Form 03**): smoking history, confirmation of postmenopausal status, hysterectomy status, and assessment for history of recurrent urinary tract infection, diabetes, connective tissue disease, and various medical conditions
- Baseline Physical Exam (**Form 04**): gather height, weight, Pelvic Organ Prolapse Quantification (POP-Q) exam, uterine size, levator muscle tone and strength, investigator assessment of vaginal atrophy, and vaginal maturation index (VMI) specimen collection (see below).
- Medication Review (**Form 05**): list all medications related to treatment of incontinence and overactive bladder
- Pelvic Floor Disorder (PFD) Questionnaires (**Form 10**): *see description above in 6.1*
- Patient Global Impression of Severity (PGI-S) (**Form 11**): 1-question tool validated for urinary incontinence and modified for POP. Assesses overall impression of symptom severity related to POP.
- Vaginal Maturation Index (VMI): See also Section 5.4. A standard plastic spatula (similar to those used for a Pap smear and readily available in any gynecology clinic) will be used to sample the upper vaginal walls for 15-30 seconds. The spatula will be swirled in a ThinPrep® container (labeled with a preprinted barcode label with a Specimen ID linked with the participant's Subject ID number), which is then stable when stored at room temperature or 4°C and shipped with cold packs in a cold shipping box for storage at UTSW.
- Blood serum collection: Blood will be drawn into a standard red top tube. 5mL (1 teaspoon) is gathered to assess baseline estrone (E1) and estradiol (E2) levels.
 - Tube: Red top glass, no additive, no clot activator with uncoated interior, vacutainer tubes (BD366430 - 16 x 100 mm x 10.0 ml)

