9.2 Sample Size and Randomization

The literature reports failure by the above definition occurring in ~40% of patients with a native tissue USLS (i.e., ~60% “success”).⁶⁹ A 2-sided logrank test with an overall sample size of **188 subjects** (94 each group) achieves 80% power at a 0.05 significance level to detect a hazard ratio of 0.5188 when the proportion of those "surviving" (i.e. "successes") in the control group is **65% compared to 80%** in the treated group, **measured at 1 year**. This presumes the accrual pattern across the study time period (3 years of accrual) is uniform. This N=188 already accounts for **25%** either lost to follow-up *or non-adherent to study cream* in the control and treatment groups. Allowing for an additional **15% loss of participants** from baseline to surgery, **222 total participants** are needed.

Potential problems & alternatives:

Differences in baseline characteristics between the groups may occur by chance, but we will mitigate that risk by stratifying by clinical site, hysterectomy status, and duration since menopause (<10y & ≥10y).

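### Subaim 2c tests postoperative cystitis with an unadjusted chi-square and leaves site and baseline recurrent-UTI history unused: a valid test, with a small amount of precision given up

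*Combined protocol and SAP*

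**What the plan says.** The analysis of Subaim 2c in 9.5 is one sentence: "Proportions of participants with postoperative cystitis will be compared using chi-square". The planning claim beside it is an "improvement from a 22% cystitis rate to 10% (80% power, α 0.05"). Section 9.4.2 defines the outcome as "any prescription of antibiotics (culture-driven or empiric) for cystitis symptoms in the first postoperative month", and Form 15 records "whether symptoms were treated empirically (i.e., no urine culture) or if culture-proven".

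Two baseline factors are available and not used in the test. Section 9.2 describes "stratifying by clinical site, hysterectomy status, and duration since menopause". Section 6.2.2 lists, under Medical History (Form 03), an "assessment for history of recurrent urinary tract infection".

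No other clause in 9.5 reaches cystitis. The control for slings and bladder medication is tied to incontinence rates. The mixed logit modelling is for categorical data such as prolapse stage, with cross-sectional comparisons again by chi-square. Subaim 2d, which follows 2c directly, uses analysis of covariance with treatment and centre as factors and the baseline value as covariate.

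**The concern.** A test that ignores a randomisation stratum or a prognostic baseline variable does not use the precision those factors offer. Two features make the question worth asking here. The outcome counts empiric prescriptions, so its rate could vary with prescribing practice at the three sites. Events will also be few: about 30 in total at the planned rates. The plan already adjusts for centre and baseline in 2d and gives no reason for treating 2c differently.

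What is at stake is a few points of power at most, and an effect estimate that matches the stratified design. As written, 2c names a test but no effect measure and no interval.

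**Working it through.** **Inputs.** From the documents: rates 22% and 10%, α 0.05 (9.5); 222 randomised, 111 per arm (Précis); 94 per arm after loss before surgery (9.2); 100 per arm under the 10% loss used for Aim 3 (9.5); three sites. Sidedness is not stated for 2c. I take it as two-sided, as for the primary test. Assumed, because the documents are silent: prevalence of recurrent-UTI history, its odds ratio (OR), and the spread between sites.

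**Step 1: the plan's own figure.** Pooled-variance formula, mean rate 0.16:

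- n per arm = [1.960·√(2·0.16·0.84) + 0.842·√(0.22·0.78 + 0.10·0.90)]² / 0.12² = (1.016 + 0.430)² / 0.0144, which rounds up to 146.
- Power at 94 per arm = Φ[(0.12·√94 − 1.016)/0.511] = Φ(0.288) = 61.3%. The same formula gives 64.0% at 100 and 68.6% at 111.

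The stated 80% does not reproduce two-sided. The nearest match is a one-sided test on all 222 randomised (79.0%). Simulated chi-square power at 94 per arm is about 62%, and this is the baseline used below.

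**Step 2: expected events.** 94 × 0.22 = 20.7 and 94 × 0.10 = 9.4, about 30 in total.

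**Step 3: chi-square against CMH.** Simulated trials had 94 per arm, three equal sites and allocation balanced within site, with marginal rates held at 22% and 10%. The CMH test used the six site-by-history strata. There were 4,000 to 40,000 trials per scenario. Site spread is the OR between the lowest and highest site; adjacent sites differ by its square root.

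| History prevalence | History OR | Site spread (OR) | Chi-square power | CMH power |
|---|---|---|---|---|
| inert | 1 | 1 | 62.3% | 61.7% |
| 10% | 2 | 1 | 63.5% | 62.7% |
| 10% | 3 | 1.8 | 62.0% | 62.3% |
| 15% | 3 | 2 | 62.3% | 62.6% |
| 20% | 3 | 2.25 | about 62% | 63.2% |
| 20% | 3 | 2.7 | 60.5% | 62.4% |
| 20% | 3 | 4 | about 62% | 63.6% |
| 25% | 5 | 4.1 | 61.2% | 65.5% |
| 30% | 6 | 2.25 | about 62% | 66.5% |
| 30% | 6 | 4 | about 62% | 67.2% |

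Monte Carlo error is about 0.7 point for the 4,000-trial rows (spread 1 with history OR 2, and spreads 1.8, 2.7 and 4.1) and smaller elsewhere. Across all runs CMH power lay between about 61% and 68%, a change of about -1 to +5 points. A further run of 40,000 trials per scenario agreed. At a history OR of 6 it showed a gain of about 3 points already at 15% prevalence, so the OR matters more than the prevalence. At 111 per arm the pattern is the same: 69.0% against 68.4% in the weakest scenario, 70.9% against 74.3% in the strongest.

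**Step 4: type I error.** With allocation balanced within site, the chi-square uses the pooled variance 0.22 × 0.78 = 0.1716, although the between-site part does not contribute to the arm difference.

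- Spread OR 4: site rates about 11.4%, 20.5% and 34.0%. Between-site variance ≈ (0.106² + 0.015² + 0.120²)/3 = 0.0086. True-to-assumed variance ratio 1 − 0.0086/0.1716 = 0.950. Effective cut-off 1.960/√0.950 = 2.011, an error of about 4.4%.
- Spread OR 2: site rates about 16.3%, 21.6% and 28.1%. Between-site variance ≈ 0.0023, ratio 0.986, effective cut-off 1.973, an error of about 4.8%.

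Simulation agrees: about 4.1% to 4.5% at spread 4 (up to 4.7% in some scenarios), and about 5% at spread 2.

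**Step 5: could adjustment deliver 80%?** It would have to explain 1 − 111/146 = 24% of the outcome variance at 111 per arm, or 1 − 94/146 = 36% at 94. No scenario came near this.

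**The case against.** The strongest reply is that nothing in the sentence is wrong. A chi-square on a randomised, double-blind comparison is valid, and the choice is pre-specified. Allocation is balanced within site and assessors are blinded, so prescribing differences between sites cannot favour an arm. Form 15 separates empiric from culture-proven treatment, so dependence on prescribing can be examined. All of this stands.

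So do three limits on the size of the point. No passage says how strongly recurrent-UTI history predicts early cystitis; 6.2.2 only lists it among the history items. Site variation in prescribing follows plausibly from the outcome definition, but no site rates are given. In ordinary scenarios the gain is a few tenths of a point.

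A reader might infer more from the same facts, and the documents do not support it:

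- That the unadjusted test is biased or invalid. It is neither; ignoring a stratum makes it at most conservative.
- That it is materially conservative. That needs the lowest and highest sites to differ by an odds ratio of about 4, roughly 11% against 34%.
- That adjustment would rescue the stated 80% power. It would not in any scenario tried.

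What the reply does not answer is why 2d adjusts for centre and baseline while 2c does not, or why 2c has no effect estimate. The change is nearly free.

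**Conclusion.** The point holds as a minor refinement to one secondary outcome. The plan leaves out of the cystitis comparison a stratification factor and a relevant baseline variable that it already has.

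The expected benefit at 94 per arm is between a loss of about 1 point of power and a gain of about 5, from a base of about 62%. At a history odds ratio of 3 it is around 1 point or less when sites differ by an odds ratio of up to about 2, and up to about 2 points with wider spread. Gains of 3 points or more appeared only with the history odds ratio set at about 5 to 6. These figures rest on assumed prevalence, odds ratios and site spread, on equal-sized sites and on a two-sided test.

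The shortfall against the stated 80% is a separate and larger problem, and this change does not repair it.

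**What to change.** In 9.5, Subaim 2c, replace the chi-square sentence with wording such as: *The proportions with postoperative cystitis will be compared by a two-sided Cochran-Mantel-Haenszel test stratified by site and baseline history of recurrent UTI (Form 03, yes/no). The Mantel-Haenszel stratum-weighted risk difference will be reported with its 95% confidence interval.* State how a missing history will be classified.

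Do not offer, as an alternative, a logistic model with every randomisation factor. Treatment, two site terms, history, hysterectomy status and menopause duration make 6 terms on about 30 expected events, or 5 per term. The plan's own rule of thumb in 9.5 is 10.

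The cost is a line or two of text. The data are already collected and no procedure changes. The downside is up to about 1 point of power if both factors prove inert. Make the change before the randomisation codes are broken, so that the covariate choice cannot depend on results.

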Aim 3 Outcomes: If there is 10% loss of patients from randomization (baseline) to surgery, there will still be 100 patients per arm eligible for the standardized intraoperative apical anterior vaginal wall surgical biopsy. Our pilot trial (Section 2.2a, *Humans*) indicates sufficient power to determine 2-fold differences in collagen subtypes and MMP activity using tissues from UTSW. Further, with ~42 samples from UTSW (21 in each group), this will provide 80% power to also detect 2-fold differences in LOX protein and mRNA expression. All Aim 3 outcomes of interest (e.g. histological wall thicknesses, qPCR-determined relative mRNA levels, collagen subtypes and elastic fiber content, collagenase and protease activity) will be summarized using the following statistics: mean, standard deviation, median, minimum and maximum. Additionally, because most biomarkers are not normally distributed, the geometric mean and standard deviation based on natural log transformed values will also be calculated. Summaries will be constructed by treatment group (CE vs. placebo) and comparisons conducted using 2-tailed Student’s *t*-tests comparing natural log transformed levels. Because this translational study (Aim 3) is considered to be descriptive and a relatively large number of markers are being considered, all p-values will be presented without adjustment for multiple comparisons and should be interpreted accordingly. We will correlate any treatment-group differences in vaginal wall or smooth muscle histomorphology, ERs, collagen gene expression, and protease downregulation with *clinical outcomes*, namely, objective or subjective “success” as outlined in Aims 1 and 2.

Ideally, CE cream application will support an improvement in prolapse recurrence success/failure rates 1y postop, but even if CE cream has a null or non-significant effect, the entire population will be divided into prolapse repair failures (*cases*) and successes (*controls*), and, controlling for CE cream exposure, univariate comparisons will be made of the continuous outcomes from Aim 3 (2-tailed Student’s *t*-tests). Those variables that attain a significance level of 0.1 or less in univariate analyses will be considered jointly in a multivariable backward stepwise logistic regression model. An accepted “rule of thumb”

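### Subaim 2c: the stated 80% power for cystitis at 22% versus 10% is about 61% at the planned 94 women per arm (two-sided 5%); 80% would need 146 per arm

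*Combined protocol and SAP*

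**What the plan says.** Section 9.5, Subaim 2c, compares cystitis proportions by chi-square and states that "this study will have sufficient power to demonstrate an improvement from a 22% cystitis rate to 10% (80% power, α 0.05"). No number per arm and no sidedness accompany the figure. Section 9.4.2 defines the outcome broadly, to "include any prescription of antibiotics (culture-driven or empiric) for cystitis symptoms in the first postoperative month".

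The sample sizes available to this comparison are given elsewhere:

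- Section 9.2: "A 2-sided logrank test with an overall sample size of 188 subjects (94 each group"), followed by "Allowing for an additional 15% loss of participants from baseline to surgery, 222 total participants are needed".
- Section 9.5, Aim 3: "If there is 10% loss of patients from randomization (baseline) to surgery, there will still be 100 patients per arm".
- Précis: 222 randomised, 111 per arm.

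Three neighbouring statements also matter. For Subaim 2a, the stress-incontinent subgroup is "expected to be at least 60%, or 67 participants per study arm", and for the UDI-6 score "65 participants are needed per arm". The text on 2a and 2b then concludes that "enrollment goals designed to address the primary aim (Aim 1) are sufficient to address these important secondary aims". For Aim 3, section 9.5 applies a rule of 10 failures per predictor to an expected 67 failures and says that this supports at least 7 variables.

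**The concern.** Halving a 22% rate with roughly 100 women per arm is a demanding target, and 80% power looked too high. Without a stated number or sidedness, a reader cannot tell which calculation produced it.

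Postoperative cystitis is a named secondary objective. If the comparison is null, the result will be read against a claim that a true fall from 22% to 10% would be detected four times in five. If actual power is nearer 60%, that reading gives the null result more weight than it deserves.

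**Working it through.** **Inputs.** Rates p1 = 0.22 and p2 = 0.10, α = 0.05 and the chi-square test come from section 9.5, Subaim 2c. The numbers per arm are 94 (9.2), 100 (9.5, Aim 3) and 111 (Précis). The 94 is the number left after the 15% pre-surgery loss: 222 × 0.85 = 188.7, and the plan uses 188.

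**Formula.** Two proportions, equal arms, pooled variance under the null:

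- Mean rate = (0.22 + 0.10)/2 = 0.16
- A = √(2 × 0.16 × 0.84) = 0.5185
- B = √(0.22 × 0.78 + 0.10 × 0.90) = 0.5115
- Power = Φ[(0.12√n − z × A)/B]
- n per arm for 80% power = [(z × A + 0.8416 × B)/0.12]²

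**Trying to reproduce the plan's 80%.** With z = 1.960 (two-sided):

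- n = 94: (1.1634 − 1.0162)/0.5115 = 0.288, power 61.3%
- n = 100: (1.2000 − 1.0162)/0.5115 = 0.359, power 64.0%
- n = 111: (1.2643 − 1.0162)/0.5115 = 0.485, power 68.6%
- n for 80%: (1.0162 + 0.4305)²/0.0144 = 145.3, so 146 per arm, 292 in total

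With z = 1.645 (one-sided), 80% needs 114.4, so 115 per arm.

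| Women per arm | Two-sided, formula | Two-sided, exact | One-sided, formula | One-sided, exact | Treated rate detectable from 22% (80%, two-sided) |
|---|---|---|---|---|---|
| 94 | 61% | 62% | 73% | 73% | 7.6% |
| 100 | 64% | 65% | 75% | 76% | 7.9% |
| 111 | 69% | 70% | 79% | 80% | 8.5% |

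The exact columns enumerate all outcomes of the uncorrected chi-square. A continuity correction lowers two-sided power to 55%, 57% and 63% and raises the requirement to 162 per arm. Unpooled and arcsine formulas stay within about 1.5 percentage points of the pooled one. Every two-sided version at 94 to 111 per arm lies between 55% and 70%, so the choice of formula does not explain the gap. The only route to 79-80% is one-sided with all 111 per arm.

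**Which sidedness does the plan use?** For the UDI-6 in Subaim 2a, the effect is (7.90 − 6.95)/1.91 = 0.497 SD. A two-sample t-test at 80% power needs 64.4 per arm two-sided, which rounds up to the stated 65. One-sided it needs 50.7, so 51. The logrank test in 9.2 and the Aim 3 t-tests are stated as two-sided.

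**Smaller points.**

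- (a) Loss from baseline to surgery is 15% in 9.2 and 10% under Aim 3 in 9.5.
- (b) The 67 for Subaim 2a is 0.60 × 111 = 66.6, that is, 60% of everyone randomised. Against 65 needed, the margin is 1 − 65/67 = 3.0%. At the 60% floor, if women lost before surgery also miss the preoperative questionnaire, 0.60 × 94 = 56.4 to 0.60 × 100 = 60 remain. Power by the plan's two-sample method is then 74% (56) to 77% (60), against 81.5% at 67.
- (c) For Aim 3, 222 × 0.75 × 0.40 = 66.6 failures. At 10 per predictor this supports 6 whole predictors, not 7.

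**The case against.** The best defence is that the 80% can be recovered. One-sided at 5% with all 111 per arm, power is 79% by formula and 80% by exact enumeration. Section 9.5 gives only α 0.05, and its wording about an improvement is directional, so this is a plausible origin of the figure. On that reading the defect is an unstated number and sidedness. This stands as an explanation but does not rescue the claim. It needs a one-sided test, which does not fit a chi-square or the plan's other calculations, and it needs no loss before surgery, against the stated 15% and 10%. Even one-sided, power is 73% at 94 per arm and 75% at 100.

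A second argument is that little depends on this. Cystitis is one of several secondary outcomes, enrolment is set by Aim 1, and the sufficiency sentence for 2a and 2b does not rest on 2c. A reported confidence interval would show the imprecision in any case. That is fair, and it limits the consequence to interpretation.

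The smaller points are weaker still. The 10% loss is worded as a conditional scenario. The 2a figure is a floor, and its shortfall disappears if prevalence is 65/94 = 69% (or 65/100 = 65%), if women lost before surgery still complete the questionnaire, or with a moderate baseline correlation. The Aim 3 count is a rounding slip in a rule of thumb for an exploratory model. These are matters of disclosure and consistency and carry no weight in the main conclusion.

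**Conclusion.** The concern holds. With a two-sided 5% test, the stated 80% power for 22% versus 10% is not reached at any number of women the plan can have. It is about 61% at 94 per arm, 64% at 100 and at most 69-70% at 111. The chance of missing a true difference of that size is about 39% at the planned number, and still 30-31% if all 222 women have surgery.

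The result assumes the plan's own rates, equal arms, and 94 per arm as the number reaching surgery, with no further loss in the first month. The two-sided reading is inferred from the named test and the neighbouring calculations, since Subaim 2c does not state it. Confidence in the 2c arithmetic is high. Of the smaller points, (c) follows directly from the plan's own rule, (a) is a plain inconsistency, and (b) is conditional. Subaim 2b, the LOX power statement, enrolment and the primary analysis are not in question. The correction should be made.

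**What to change.** In section 9.5, Subaim 2c, state the number per arm and that the test is two-sided. Then give either about 61% power for 22% versus 10%, or 80% power for 22% versus about 7.6%, both at 94 per arm.

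At the same time:

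- (a) Use one baseline-to-surgery loss rate in 9.2 and in the Aim 3 text of 9.5.
- (b) For Subaim 2a, state the assumed loss before the preoperative questionnaire, the assumed prevalence of stress incontinence, and any baseline correlation relied on.
- (c) For Aim 3, replace 7 variables with 6. Set the final model size from the failures observed among women with the marker measured, counting CE exposure as a degree of freedom if it is in the model.

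The cost is wording in 9.2 and 9.5. Enrolment, data collection and the primary analysis do not change. The stated power for cystitis becomes less favourable.
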